- 5) To explore the effects of an early literacy promotion program compared to standard literacy promotion on social-emotional development among poor urban children in Philadelphia.

Study Design:

A randomized controlled trial will be conducted comparing two versions of the parent-child reading program: Early literacy promotion (ELP) and Standard Literacy promotion (SLP). An additional sub-study will utilize semi-structured interviews with a purposive number of parents enrolled in the study to explore barriers and promoters to reading to their children.

Setting/Participants:

We will recruit participants who are English or Spanish speakers, at least 15 years old, the parent of a child born ≥ 35 weeks gestation age and < 4 weeks at enrollment and with Medicaid insurance. We will be recruiting from one urban site affiliated with CHOP (Karabots). The combined total enrollment number of participants will be 240 (120 dyads of parent and infant). The target enrollment number of participants for the sub-study will be up to 30 parents.

Study Interventions and Measures:

In this intervention, parents/children randomized to the ELP arm will receive a book with developmentally appropriate advice about reading at each well child visit from one week through 5 months of age, as well as weekly text reminders related to reading. Those in the SLP arm will receive weekly text messages about child safety. From 6 months of age, both groups will receive SLP and will attend study visits every six months until age 2. Difference between the groups on the PLS (Pre-school language score-5th edition) score at 6 and 24 months of age are the main outcomes. StimQ score differences at 6,12,18, and 24 months of age will be a secondary outcome. Other outcomes include score differences at 12, 18, and 24 months in the PHQ-9 and the PSI-Short Form, and differences in the ITSEA at 18 and 24 months. A purposive sample of parents will participate in a qualitative interview component to understand barriers to reading, parents' perceptions of the value of reading to infants, and factors which promote reading.

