Children in both study arms will be followed every 6 months until age 2. Parents will complete study measures consisting of demographic characteristics, postpartum depression symptoms, health literacy, and adverse childhood experiences at enrollment, and parents and children will complete measures of reading activity (Stim-Q), and child expressive and receptive language development (Preschool Language Scale-V) at 6, and 24 months of age. At 12, 18, and 24 months, measures of parental stress (PSI-Short Form, Appendix 9), parental depression (PHQ-9, Appendix 10) will be collected. Child social and emotional competencies will be collected at 18

and 24 months of age (ITSEA, Appendix 11). Information on reading activities and expressive and receptive language outcomes will be collected in concert with scheduled well child visits. Differences in reading activities, parental mental health, child's social/emotional competencies, and language outcomes will be assessed between groups using intention-to-treat analysis. The EHR will be reviewed for children in both arms to count the number of well child visits and examine their vaccination history.

Parents of children who are participating in the study will be informed of the results of their PLS testing in writing. Those whose children score less than 1.5 standard deviations below the mean will be informed that their children's language development is within the average range. Parents whose children who score 1.5 standard deviations or greater below the mean will be informed that their child is exhibiting delays in language development and will be referred for additional evaluations and/or services. In addition, the child's clinician will be informed of their result.

Responses to the question on the PHQ-9 will be checked to determine whether the caregiver has endorsed suicidal ideation. If they have endorsed any of the suicide questions, research staff will administer additional follow up questions and call the study licensed psychiatrist to determine course of action (see Appendix 13-Suicide Protocol). This procedure has been implemented successfully in other studies of parental depression. During the study visits, if a participant was to endorse suicidal ideations, the Appendix 13: 'Suicide Protocol' will be followed to maximize the safety of the participant. At any time, caregivers who endorse suicidal ideations will require immediate follow up with the licensed psychiatrist on call.

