 - Parents will complete measures of reading activity (Stim-Q) at each study visit.
 - Children will complete measure of child expressive and receptive language development (Preschool Language Scale-V) at 6- and 24-month visits.
 - At the 12-, 18-, and 24-month visits, parents will complete the PSI and PHQ-9 questionnaires.
 - At the 18- and 24-month visits, parents will also complete the ITSEA about their child.

4) STUDY EVALUATIONS AND MEASUREMENTS

a. Screening and Monitoring Evaluations and Measurements

i. Parent Adversity (ACE)

The 9 ACE questions query adults as to their exposure to 9 different adverse childhood experiences (economic hardship, domestic violence, parent mental health, discrimination, parent substance abuse, divorce, parent death, parent incarceration, and neighborhood violence) and are contained in the 2011-12 National Survey of Children's Health, a nationally representative telephone survey.

ii. Parent Health Literacy (SAHL)

The Short Assessment of Health Literacy (SAHL) is a validated measure of health literacy for English- and Spanish-speaking populations.

iii. Parent Depressive Symptoms (EPDS)

The Edinburgh Postnatal Depression Scale (EPDS) is a validated 10-item scale for postpartum depression symptoms with scores ≥ 9 having a sensitivity of 97% and specificity of 43% for major or minor depression.

iv. Reading Activity (StimQ)

The StimQ is an office measure of cognitive stimulation at home available in Spanish and English, and the Read subscale of the StimQ contains questions on the frequency of parent-child reading activity and the number and variety of books at home.²⁴ Psychometric analysis of the StimQ shows high internal consistency (Cronbach's Alpha=0.89) and test-retest reliability ($r=0.84$) and moderate correlation with the Bayley Scales of Infant Development ($r=0.52$, $p<0.001$).

We will also use a brief reading questionnaire (Appendix 12) about when participants began reading to their child and what influenced that decision.

v. Language Development (PLS)

The Preschool Language Scale-5th Edition (PLS) is a validated measure of expressive and receptive language function among children from birth through 7 years of age and is available in Spanish and English. The PLS has been standardized in over 1400 children nationally with a sensitivity of 0.83 and a specificity of 0.80 for the detection of language delay.

vi. Infant Toddler Social Emotional Assessment (ITSEA)

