The primary endpoint will be differences in PLS scores at 6 and 24 months of age.

b. Secondary Endpoints

Secondary endpoints will be the difference in StimQ scores at 6, 12, 18, and 24 months of age and the ITSEA scores at 18 and 24 months of age.

c. Statistical Methods

Summary statistics will be obtained, and differences between intervention and control groups will be assessed using intention-to-treat analysis. Cross-sectional differences in StimQ scores and PLS scores between intervention and control groups at the 6 and 24 month study visits and differences in ITSEA scores at 18 and 24 month study visits will be assessed using t-tests. To determine whether early literacy promotion is associated with greater language development, we will develop regression models using longitudinal data methods that adjust for correlation in PLS scores over time and for potential confounding by demographic characteristics. To explore whether early literacy promotion is associated with greater child socio-emotional development, we will develop regression models for scores at 18 and 24 months that adjust for potential confounding by demographic characteristics. To explore the impact of early literacy on healthcare utilization, the EHR will be reviewed to identify a subjects number of well visits and their vaccination history.

To determine whether parent adversity, health literacy, parenting stress, and/or depression modify the effects of early literacy promotion on language development, we will develop similar regression models using longitudinal data methods, but we will also fit interaction terms between study group and ACE score (≥ 4), SAHL (high or low), PSI score, and EPDS score (> 9) or PHQ-9 Score (> 4). To determine if parent-child reading activity mediates the association of intervention group assignment and language development, we will use mediation analysis with separate models regressing group assignment on language development, parent-child reading activity on group assignment, and group assignment on language development adjusted for parent-child reading activity.

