7.2 Adverse Event Reporting

Since the study procedures are not greater than minimal risk, SAEs are not expected. If any unanticipated problems related to the research involving risks to subjects or others happen during the course of this study (including SAEs) they will be reported to the IRB in accordance with CHOP IRB SOP 408: Unanticipated Problems Involving Risks to Subjects. AEs that are not serious but that are notable and could involve risks to subjects will be summarized in narrative or other format and submitted to the IRB at the time of continuing review. We will query participants concerning any disclosures of PHI at each study visit. We will only query participants once concerning childhood trauma and depressive symptoms at the baseline visit.

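### Aim 2 tests PSI and PHQ-9 as modifiers of the ELP effect on PLS, but both are first measured at 12 months, after the 6-month PLS, and no visit is named

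*Combined protocol and SAP*

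**What the plan says.** Specific Aim 2 (section 2.2) asks whether parental adversity, health literacy, parenting stress and depression moderate the ELP effect. Section 5c gives the analysis: "we will develop similar regression models using longitudinal data methods, but we will also fit interaction terms between study group and" ACE (cut at 4), SAHL (high or low), "PSI score, and EPDS score (> 9) or PHQ-9 Score (> 4"). The word similar points back to the main language model, described as "regression models using longitudinal data methods that adjust for correlation in PLS scores over time". PLS is scheduled at 6 and 24 months.

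The schedule for the two parent scores is the same wherever it appears. Section 3.1.2 says "At 12, 18, and 24 months, measures of parental stress (PSI-Short Form, Appendix 9), parental depression (PHQ-9, Appendix 10) will be collected". The follow-up visit list (Study Procedures, part c) says "At the 12-, 18-, and 24-month visits, parents will complete the PSI and PHQ-9 questionnaires". The enrolment battery in section 3.1.2 is "demographic characteristics, postpartum depression symptoms, health literacy, and adverse childhood experiences at enrollment", with no PSI and no PHQ-9. Section 3.1.1 places the EPDS before the intervention.

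The Abstract states "From 6 months of age, both groups will receive SLP", and lists between-arm differences in PHQ-9 and PSI at 12, 18 and 24 months among the other outcomes. Section 9 plans a separate moderator paper on whether ELP helps some high-risk groups more, naming childhood adversity and mental health conditions.

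**The concern.** An effect modifier in a randomised comparison should be fixed before treatment can act on it. The group-by-modifier term then compares randomised arms within strata that treatment did not create. PSI and PHQ-9 do not meet that condition. They are first recorded six months after the arms stop differing, and the plan itself treats them as things ELP may change. PSI-SF also includes scales for parent-child dysfunctional interaction and for a difficult child (section 4, Parenting Stress Index), so it may reflect the child and the relationship that ELP targets.

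A reader of the moderator paper would take a PSI or PHQ-9 interaction as evidence about which families benefit. It could equally show that ELP, or the child's language, changed the parent's score. The plan also leaves the visit and the depression instrument open, so the analyst could choose among several versions of each term after seeing the data.

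**Working it through.** **Order of events**

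| Time | What happens |
|---|---|
| Enrolment (under 1 month) | ACE, SAHL, EPDS |
| To 6 months | The arms differ |
| 6 months | First PLS; both arms receive SLP from here |
| 12 months | First PSI and PHQ-9 |
| 18 months | PSI and PHQ-9 |
| 24 months | PSI and PHQ-9; second PLS |

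PSI and PHQ-9 have no assessment at or before the 6-month PLS. The smallest gap by which the modifier follows that outcome is 12 − 6 = 6 months. Candidate versions of each term: 3 for parenting stress (PSI at three visits) and 1 + 3 = 4 for depression (EPDS, or PHQ-9 at three visits).

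**The plan's own figure.** Section 5c gives 120 children, 60 per arm, for power 0.90, alpha 0.05, a 4-point difference and 20% loss. It gives no SD and no sidedness, so I solved for the SD. With 60 × 0.8 = 48 per arm, the normal approximation is SD = 4 × √(48/2) / (1.960 + 1.282) = 6.05. The exact t-test gives 5.98 two-sided or 6.65 one-sided. I use 6 below.

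**Size of a spurious interaction.** Assumptions: the true ELP effect is 4 points for every family, so the true interaction is zero; the correlation between parent score and PLS is −r with r = 0.3 to 0.4; 48 per arm; a single PLS assessment rather than the full longitudinal model.

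- (a) ELP does not change the score and PLS does not feed back on it: 0.
- (b) Continuous PSI, ELP shifts every score by 0.5 SD: 0. Simulation gave −0.003 and +0.006 points, with rejection of 4.9% and 5.1%.
- (c) PHQ-9 cut at a threshold, shifted by d = 0.25 to 0.5 SD. With the control cut at t SDs (t = 0, 0.5, 1; that is 50%, 31% or 16% of controls above it), the interaction is −r·SD·{[λ(t+d) − λ(t)] − [m(t+d) − m(t)]}, where λ = φ/(1 − Φ), m = −φ/Φ, and positive d means that ELP lowers the score. For t = 1, d = 0.5, r = 0.4: −2.4 × [(1.939 − 1.525) − (−0.139 + 0.288)] = −2.4 × 0.265 = −0.64 points. The SE is 3.93, so the ratio is 0.16. That case expects only 48 × 0.0668 = 3.2 ELP parents above the cut. The full range is −0.02 to −0.64 if ELP lowers scores and −0.13 to +0.39 if it raises them. Requiring at least 5 expected per cell, the extremes are −0.39 and +0.39 (0.14 SE).
- (d) Continuous score, ELP multiplies its spread by k = 0.7 to 1.3. The interaction per control SD is −r·SD·(1/k − 1). For r = 0.4, k = 0.7: −2.4 × 0.429 = −1.03 (SE 1.42, ratio 0.72, rejection 11.0%). For r = 0.4, k = 1.3: −2.4 × (−0.231) = +0.55 (SE 1.04, ratio 0.53, rejection 8.7%). Over all settings tried, rejection was 5.5% to 11.0% at a nominal 5% (40,000 simulated trials each).
- (e) PLS feeds back on the parent score, r = 0.3: 0 if continuous, −0.02 to −0.17 points if dichotomised (at most 0.05 SE).

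At an assumed SD of 15, points and SEs in (c) and (d) grow by 15/6 = 2.5 and the ratios do not change.

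**The case against.** The strongest reply is that the numbers are small. Three scenarios give exactly zero. The one closest to the reversed timing, (e), gives at most 0.05 SE. The dichotomised case (c) is swamped by its own SE. Only (d) visibly inflates error, and nothing in the documents suggests that ELP rescales the spread of parent scores. This stands as a statement about size, and the point should not be presented as a demonstrated large bias. It does not restore the meaning of the term: a near-zero bias under one assumed mechanism cannot be verified from the trial's data, and the free choice of visit and instrument is a problem under all of them.

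Second, the EPDS-or-PHQ-9 wording might mean EPDS for the 6-month PLS and PHQ-9 for the 24-month PLS. Section 5c does not say so. That reading would remove the reversed order for depression, but PHQ-9 would still be measured after the intervention, and PSI would still have no value before the 6-month PLS.

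Third, sections 3.1.1 and 3a describe randomisation before the baseline questionnaires, so ACE, SAHL and EPDS may also follow randomisation. That is fair as to wording. The distinction that matters is before or after the intervention, and section 3.1.1 places those three before it.

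Fourth, Aim 2 is exploratory, and enrolment ACE and EPDS already serve the examples in section 9. This limits the consequence, and I accept it.

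**Conclusion.** The concern holds as a matter of schedule and does not depend on the arithmetic. Followed as written, section 5c would report a possible consequence of ELP as a modifier of its effect, and for the 6-month PLS it would use a score taken at least six months after the outcome. Depression has a sound pre-intervention measure in the EPDS. Parenting stress has none, so that part of Aim 2 cannot be answered as moderation with the planned data.

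The size is uncertain: from zero to about 1 point per control SD in the scenarios tried, conditional on the assumed correlations, shifts, spreads and cuts and on the back-solved SD. The likely harm is a misread subgroup statement. The primary PLS comparison and the ACE, SAHL and EPDS interactions do not share this timing problem. The change should be made, but it does not threaten the trial's main result.

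**What to change.** In section 5c, limit the effect-modification list to ACE, SAHL and EPDS (above 9), and remove PSI and the PHQ-9 alternative. Analyse PSI and PHQ-9 as outcomes, as the Abstract already lists them. Reword Aim 2 in the Abstract and section 2.2 to say that parenting stress has no baseline measure and is not tested as a moderator.

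A lighter alternative keeps a PSI or PHQ-9 term but restricts it to the 24-month PLS, names one visit (12 or 18 months) in advance, and reports it as an association with a variable measured after the intervention.

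Separately, section 7.2 states "We will only query participants once concerning childhood trauma and depressive symptoms at the baseline visit", which conflicts with the PHQ-9 schedule in section 3.1.2 and the follow-up visit list. These passages must be reconciled.

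The cost is text edits, with no new data. The price of the first option is that parenting stress leaves Aim 2 as a moderator. Keeping it as a true moderator would need a parenting-stress measure at enrolment.

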Despite these encouraging results, poor children who participate in ROR still demonstrate language scores that are 6 to 15 points lower than national averages.¹⁷ This may be the result of delays in initiating parent-child verbal interactions until a child's 6-month well child visit. There may be reason to suspect that children exposed to more rich and intensive parent-child verbal interactions prior to six months of age may achieve greater language functioning and outcomes later on.^{19,20} For this reason, we are proposing a study to test the effects of early literacy promotion beginning by 1 month of age with standard child literacy promotion using the ROR model beginning by 6 months of age.

Adverse childhood experiences (childhood adversity) have been shown to have significant impact on the life course of individuals including mental health, chronic disease, and even early death.²¹⁻²⁵ Examples of adversity include abuse, neglect, family dysfunction, and violence, among others. Exposure to adverse childhood experiences (ACE's) is frequent and significant in disadvantaged, minority communities.²⁶ Exposure to chronic stress from adversity leads to altered neurological development and cognitive impairment.²⁷⁻²⁸ For many, adversity is chronic and continues into adulthood. A biological marker of stress is the level of cortisol. Through the measurement of cortisol levels, maternal stress has been shown to negatively impact infant cognitive development and infant-parent attachment.²⁹⁻³⁰ For parents who have chronic exposure to stress and adversity, this likely can negatively impact their interactions with their children and through this mechanism also affect the development of their children.

Understanding how parents' exposure to ACE's influence reading behavior can inform the development of future early childhood development interventions that target communities with high exposure to adversity such as poor communities. Furthermore, understanding contextual factors that influence reading behaviors among parents can serve as additional areas to address in future literacy promotion interventions.

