2.2 Secondary Objectives

Specific Aim 2: To explore whether Parent history of adversity, health literacy, parenting stress, and depression moderate the effects of early literacy promotion.

Specific Aim 3: To explore whether the effects of early literacy promotion are mediated through the intensity of reading behaviors.

Specific Aim 4: To identify perceptions of barriers to and promoters of reading behavior among parents with high and low ACE scores.

Specific Aim 5: To explore the effects of an early literacy promotion program compared to standard literacy promotion on social-emotional development among poor urban children in Philadelphia.

Specific Aim 6: To explore the impact of early literacy on healthcare utilization

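### The Aim 3 mediation models are worded with the arm as outcome and, once turned round, name no baseline covariates, visit pairing, indirect effect or interval

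*Combined protocol and SAP*

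**What the plan says.** Section 2.2 lists Aim 3 as a secondary objective: "To explore whether the effects of early literacy promotion are mediated through the intensity of reading behaviors". The only analysis text for it is one sentence in section 5c (Statistical Methods). It opens with the purpose, "To determine if parent-child reading activity mediates the association of intervention group assignment and language development", and then plans separate models "regressing group assignment on language development, parent-child reading activity on group assignment, and group assignment on language development adjusted for parent-child reading activity".

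Related text:

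- **Covariates elsewhere.** The main language model in section 5c is to "adjust for correlation in PLS scores over time and for potential confounding by demographic characteristics". The mediation sentence does not repeat this.
- **Baseline data.** Section 3.1.2: "Parents will complete study measures consisting of demographic characteristics, postpartum depression symptoms, health literacy, and adverse childhood experiences at enrollment".
- **Parenting stress.** Section 3c (Follow-up Visits): "At the 12-, 18-, and 24-month visits, parents will complete the PSI and PHQ-9 questionnaires". There is no baseline PSI.
- **Visits.** Sections 3c and 5b put StimQ at 6, 12, 18 and 24 months; section 3c puts PLS at 6 and 24 months. Section 3.1.2 can be read as placing StimQ at 6 and 24 months only. Six-month StimQ exists on either reading.
- **Reporting.** Section 9 plans a separate manuscript on mediation. It adds Reach Out and Read sessions as a possible mediator, for which section 5c has no model.

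**The concern.** The second model, reading on arm, is the right way round. In the same phrasing, the first and third regress the arm on language. A model with the randomised arm as outcome does not estimate a programme effect and cannot enter a mediation decomposition.

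Turning the models round leaves a further problem. Randomisation protects arm-to-reading and arm-to-language, but not reading-to-language. A parent characteristic that affects both how much is read and how language develops would produce an apparent indirect effect where none exists. The protocol's rationale points to candidates. On maternal stress, section 1.3 says "maternal stress has been shown to negatively impact infant cognitive development and infant-parent attachment"; on chronic stress and adversity in parents, it says "this likely can negatively impact their interactions with their children and through this mechanism also affect the development of their children". Several such measures are collected at enrolment, yet none is named for this model.

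Because no visits are paired, 6-month reading with 6-month PLS, or 24-month with 24-month, would satisfy the plan. Children with more language may be read to more, so same-visit pairs can reflect influence in the opposite direction. With no indirect effect or interval defined, the planned manuscript would rest on choices that could be made after the data are seen.

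**Working it through.** The plan gives no figure for the mediation analysis, so there is none to reproduce. The one design input used is the sample size in section 5c: 120 children less 20% loss, 120 × 0.80 = 96. Every path strength below is an assumption, in within-arm SD units, and true mediation is zero unless stated.

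**1. Confounding.** Let the arm shift reading by a, and let one parent factor act on both reading and language with strength g. Within arm, reading and language then correlate g², which the third model (direction corrected) attributes to reading.

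- Unadjusted false indirect effect: a × g².
- If baseline covariates capture a share R² of the factor: a × g² × (1 − R²) / (1 − g²R²).

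With a = 0.5. For example, at g = 0.5 and R² = 0.5: 0.125 × 0.5 / (1 − 0.125) = 0.071.

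| g | Unadjusted | Half captured | Fully captured |
|---|---|---|---|
| 0.2 | 0.020 | 0.010 | 0 |
| 0.3 | 0.045 | 0.024 | 0 |
| 0.5 | 0.125 | 0.071 | 0 |

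Share of simulated trials (96 children, percentile-bootstrap 95% interval) in which the interval wrongly excludes zero:

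- Unadjusted: 5.1%, 9.9% and 47.8% at g = 0.2, 0.3 and 0.5.
- Half captured: 5.9% at g = 0.3 and 19.3% at g = 0.5.
- Fully captured: 3.5% at g = 0.5.

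If the arm shifts reading by only 0.3 SD, the bias shrinks to 0.3 × 0.09 = 0.027 at g = 0.3 and 0.3 × 0.25 = 0.075 at g = 0.5. False positives are then about 5% and 23%, using a joint test of the two paths.

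**2. Same-visit pairs.** Let language raise reading by k = 0.3, with no effect of reading on language. Two set-ups give different answers:

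- The arm shifts reading by 0.5 SD: 0.5 × 0.3 = 0.15 SD.
- The arm shifts language by 0.5 SD and reaches reading only through language: (0.3 × 0.5) × 0.3 / (1 + 0.3²) = 0.15 × 0.275 = 0.041 SD.

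In the first set-up, pairing 6-month reading with 24-month PLS (6-to-24-month PLS correlation 0.5) gives 0.5 × 0.3 × 0.5 = 0.075 SD. Adding 6-month PLS to the model brings it to zero.

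**3. Cost of adding 6-month PLS.** Suppose reading acts on 6-month PLS at 0.3, 6-month on 24-month PLS at 0.5, and reading directly on 24-month PLS at 0.15. The true indirect effect is 0.5 × (0.15 + 0.3 × 0.5) = 0.15. With 6-month PLS in the model it is 0.5 × 0.15 = 0.075.

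**4. Precision.** With 96 children and a true indirect effect of 0.5 × 0.4 = 0.20 SD, the simulated 95% bootstrap half-width averages 0.189 SD, nearly the size of the effect.

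**The case against.** The strongest reply is that the one outright error is editorial and the rest is silence. The purpose clause and the second model already show the intended direction. The sentence lists which paths are modelled; it is not a covariate list, and it follows models that do adjust for demographics. A reader might infer that the plan has chosen to leave out demographics and to pair same-visit scores. The documents do not support that: neither choice is stated. What stands is that, even if demographics are read in, ACE, SAHL and EPDS remain unnamed and same-visit pairs are not excluded.

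A reader might also infer that section 1.3 itself asserts confounding. It does not. The passage on adversity describes a chain from adversity through interaction to development. If reading carried that whole chain, the factor would affect language only through reading, and the unadjusted model would be unbiased; a simulation of that case gave 0.000 for a true value of 0 and 0.15 for a true 0.15. Confounding needs a route outside reading. That is plausible, because interaction is broader than the reading frequency and books covered by StimQ Read, but it remains an inference. The sentence on maternal stress is more direct, but parenting stress is not measured at baseline.

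It is also fair that no path strength comes from the documents, that false positives are about nominal at 0.2 SD, and that section 5c names no confidence interval for any analysis, so that gap is not special to mediation.

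**Conclusion.** The point holds as a minor one on an exploratory aim. The first and third models need their direction corrected. With that done, the named adjustment on the unrandomised path is reading alone, the visit pairing is unstated, and the indirect effect and its interval are undefined, so the result is open to bias.

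How much bias is unknown. With no true mediation and a 0.5 SD arm effect on reading, a common cause of 0.2 to 0.5 SD gives about 0.02 to 0.125 SD and false positives from about 5% to 48%; both are lower if the arm moves reading less. Same-visit feedback of 0.3 gives about 0.04 to 0.15 SD, depending on the set-up. These figures show that bias is possible. They do not estimate it for this trial, and the upper figures should not be read as expected values.

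Nor does the point reach the trial's main conclusion: the randomised PLS comparison does not use these models. It is worth correcting because section 9 plans a manuscript on the result and the repair uses data already being collected.

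**What to change.** Replace the mediation sentence in section 5c with three models, run separately for the PLS expressive and receptive subscales:

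1. 24-month PLS on arm (the total effect, which the plan already intends).
2. 6-month StimQ Read on arm.
3. 24-month PLS on arm and 6-month StimQ Read.

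Include baseline ACE, SAHL, EPDS and the main language model's demographic characteristics in all three. Section 5c does not list those characteristics, so the list should be written down. Six-month reading fits because the arms receive different literacy promotion only before 6 months, and it precedes the outcome.

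The main estimate is the arm coefficient in (2) times the reading coefficient in (3), with a percentile-bootstrap 95% interval. Adding 6-month PLS to (3) is a sensitivity analysis only. State the assumptions: no unmeasured common cause of reading and language (parenting stress is first measured at 12 months) and no arm-by-reading interaction. In section 9, limit the mediator to reading, or label Reach Out and Read sessions as post hoc.

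The cost is SAP wording and a few lines of code, with no new data. The downsides are that 6-month PLS is no longer a mediation outcome, 12- and 18-month StimQ go unused in this model, the main model can keep some reverse-influence bias, and the sensitivity model can remove part of a real early effect.
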